1.3 SCHEDULE OF ACTIVITIES

Treatment Group 1

| Treatment Group 1 | Screening | Time 1 (Home Visit 1) Week 1: (within 42 days of screening) | Time 2 Week 4: (± 7 Days) | Time 3 Week 8: (± 7 Days) | Time 4 (Home Visit 2) Week 12: (± 14 Days) | Time 5 Week 16: (± 7 Days) | Time 6 Week 20: (± 7 Days) | Time 7 (Home Visit 3) Week 24: (± 14 Days) |
|-------------------------------------|-----------|--|---------------------------------|---------------------------------|---|----------------------------------|----------------------------------|---|
| Screen for eligibility | X | | | | | | | |
| Obtain verbal informed consent | X | | | | | | | |
| Schedule Visit 1 | X | | | | | | | |
| Obtain written informed consent | | X | | | | | | |
| Care Partner Questionnaire | | X | | | X | | | X |
| Study Participant Questionnaire | | X | | | X | | | X |
| Oral Health Evaluation | | X | | | X | | | X |
| ADCS-ADL | | X | | | | | | |
| Oral Hygiene Skill Assessment Sheet | | X | | | X | | | X |
| Coaching Module | | | | | | | | |
| Tailored Oral Hygiene Instruction | | | | | | | | |

| Treatment Group 1 | Screening | Time 1 (Home Visit 1) Week 1: (within 42 days of screening) | Time 2 Week 4: (± 7 Days) | Time 3 Week 8: (± 7 Days) | Time 4 (Home Visit 2) Week 12: (± 14 Days) | Time 5 Week 16: (± 7 Days) | Time 6 Week 20: (± 7 Days) | Time 7 (Home Visit 3) Week 24: (± 14 Days) |
|---|-----------|--|---------------------------------|---------------------------------|---|----------------------------------|----------------------------------|---|
| Montreal Cognitive Assessment (MoCA) | | X | | | X | | | X |
| Educational booklet provided | | X | | | | | | |
| Electronic Toothbrush Data Download | | | X | X | X | X | X | X |
| Detailed explanation of education booklet | | | | | | | | X |
| Exit Interview w/participant | | | | | | | | X |
| Exit Interview w/care partner | | | | | | | | X (via phone) |

Treatment Group 2

| Treatment Group 2 | Screening | Time 1 (Home Visit 1) Week 1: (within 42 days) | Time 2 Week 4: (± 7 Days) | Time 3 Week 8: (± 7 Days) | Time 4 (Home Visit 2) Week 12: (± 14 Days) | Time 5 Week 16: (± 7 Days) | Time 6 Week 20: (± 7 Days) | Time 7 (Home Visit 3) Week 24: (± 14 Days) |
|---------------------------------|-----------|---|---------------------------------|---------------------------------|---|----------------------------------|----------------------------------|---|
| Screen for eligibility | X | | | | | | | |

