Participants in Treatment Group 1 and Treatment Group 2 will receive two smart electronic toothbrushes that collect the time, date and duration of brushing (each toothbrush stores approximately 15 days of the brushing data). The study coordinator will download the toothbrush data on a monthly basis to allow sufficient memory storage space for subsequent data collection. Participants in Treatment Group 2 will be asked to self-report oral hygiene behavior using a calendar log throughout the study. They will also receive individualized instruction on oral hygiene technique, cueing strategy development, oral hygiene monitoring, and coaching four times over the course of the first 3 months of the study. One module is delivered at the first visit, the next 2 are delivered telephonically at 1 month and 2-month time points, and the final module is delivered at home visit 2.

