Clinical Oral Health Evaluation. (All groups) The hygienist performs an oral health evaluation (see detailed procedures in Section 8.1 Endpoint and other Non-Safety Assessments). The evaluation is used by the hygienist to guide tailored recommendations for the treatment plan for participants assigned to Treatment Group 2.

Assessment of technical and adaptive challenges and instruction. (Treatment Group 2) This assessment is completed in the location where the dyad normally does oral care, usually a bathroom with a large mirror over the sink. Because the interventionist and the care partner must integrate the tailored instruction, they both will observe. Standing in front of a mirror, the dental hygienist will ask the participant to brush using his/her normal toothbrush to assess the participant's toothbrushing technique and begin to identify technical challenges and areas for specific feedback on technique, including areas of the dentition missed in brushing. S/he will then demonstrate the proper technique on a mouth model using a smart electronic toothbrush. Standing in front of a mirror, participant will then be asked to brush her/his teeth again, using the smart electronic toothbrush and the technique demonstrated. This approach is based on the approach developed by others³² for the clinical setting and adapted for the in-home setting. We will recommend use of interdental cleaning aids. Using the same approach as above, the hygienist will assess interdental cleaning by participants and assess cleaning partial dentures, if applicable. The hygienist will demonstrate the correct cleaning techniques and ask the participant to return-demonstrate. The participant and care partner will then be shown how to use a disclosing tablet to identify areas of dentition missed in brushing. The care partner is given an electronic toothbrush to support the collaborative effort of the dyad in regular and appropriate oral hygiene behavior. The care partner is also asked to demonstrate use of the electronic toothbrush to ensure that s/he understands. The oral hygiene technique assessment will be conducted at each visit. Examples of technical challenges that might be identified include limited hand dexterity which will guide selection of the right tool for interdental cleaning, or gum conditions that might guide recommendations

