- Participant oral hygiene behavior (investigator developed) asks about the participants' frequency of toothbrushing and flossing. The response categories will be coded as 1= Twice a day or more, 2=once a day, 3= Several times a week, 4= Once or less than once a week, 5=Hardly ever, and 6= Never. This measure also includes the frequency of reminders that the care partner provides. The response categories include 1=Very often, 2=Sometimes, 3=Occasionally, and 4= Not at all
- Own oral hygiene behavior (investigator developed) asks about care partners' frequency of toothbrushing, flossing, and mouth rinse. The response categories will be coded as 1= Twice a day or more, 2=once a day, 3= Several times a week, 4= Once or less than once a week, 5=Hardly ever, and 6= Never.

Study coordinator collects data from log and a smart toothbrush

- Oral hygiene behavior data collected from log for Treatment Group 2: Duration of toothbrushing and frequency of toothbrush. Duration of brushing will be measured as a continuous variable; frequency will be coded as an ordinal variable, 1-3.
- Oral hygiene behavior data from a smart toothbrush for Treatment Group 1 and 2: Duration of toothbrushing and frequency of toothbrushing. Duration of brushing will be measured as a continuous variable; frequency will be measured as a continuous variable..

After both sets of questionnaires are completed, the dental hygienist will perform a complete oral health evaluation on the participant:

- Determination of missing teeth (Number of missing teeth coded as a continuous variable.)
- Plaque Index⁴⁴ using UNC Modified Green and Vermillion Oral Hygiene Index (1960) Plaque will be measured as 0= No plaque, 1=Plaque covers < 1/3 tooth, 2=Plaque covers >=1/3 but < 2/3 tooth, and 3=Plaque covers >=2/3 tooth.

- Gingival Index⁴⁵ using UNC Modified Loe and Silness Gingival Index. Gingival inflammation is classified as 0 = Normal gingiva, 1 = Mild inflammation, no bleeding on probing, 2 = Moderate inflammation, bleeding on probing, 3 = Severe inflammation, tendency to spontaneous bleeding.

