Electronic Toothbrush Data. The secondary outcomes of participants' frequency and duration of toothbrushing was also measured via electronic toothbrush for participants randomized to **TG1** or **TG2**, at baseline, 3 months and 6 months post-randomization. We anticipate a substantial proportion of participants may have missing data for frequency and duration of toothbrushing due to toothbrush device issues (e.g. battery, glitches etc.). Following the identification and removal of test cases in the dataset, we will examine outliers and missing data patterns via visualization to inform subsequent strategies. Our primary goal is to identify a subset of participants with complete data for frequency and duration of toothbrushing in the electronic toothbrush dataset. These data will be used as a validation set to examine agreement between participant self-report, care-partner report, and electronic toothbrush-assessed frequency and duration of toothbrushing. To align with the care-partner and participant reported toothbrushing data, we will calculate an average measure for frequency and duration based on 6 days of consecutive or non-consecutive data, surrounding the baseline, 3 month, and 6 month assessment date, which will serve as the index date for each visit. Lastly, we will compute relevant interclass correlation coefficients to explore agreement between participant self-report, care-partner report, and electronic toothbrush assessed frequency and duration of toothbrushing.

Descriptive Tables

Table 1. Participant demographics by arm at baseline.

- Variables for inclusion: age, sex, education, race, oral health knowledge score, ADL score, MOCA score

Table 2. Care-partner demographics by arm at baseline.

- Variables for inclusion: age, sex, education, race, oral health knowledge score

Table 3. Primary and secondary outcomes by arm at baseline, 3 months, and 6 months.

- Variables for inclusion: frequency toothbrushing, duration of toothbrushing, frequency of interdental cleaning, interproximal cleaning technique, oral hygiene skills score, oral health knowledge score.
- *Participant oral health knowledge score (separately – not a secondary outcome).*

Table 4. Exploratory mediators by arm, at baseline, 3 months, and 6 months.

- Variables for inclusion: oral care self-efficacy, leadership self-efficacy, behaviors cueing methods, leadership focused communication.

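### The planned agreement between reported and device-measured brushing has no valid baseline comparison, and the SAP leaves the common scale and the source of reported duration unstated

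*Combined protocol and SAP*

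**What the plan says.** The SAP (Supplementary Strategies, Electronic Toothbrush Data) treats participants with complete brush recordings as a validation set. For each visit, "we will calculate an average measure for frequency and duration based on 6 days of consecutive or non-consecutive data", with the days taken "surrounding the baseline, 3 month, and 6 month assessment date". It then states: "we will compute relevant interclass correlation coefficients to explore agreement between participant self-report, care-partner report, and electronic toothbrush assessed frequency and duration of toothbrushing". It does not give the form of the coefficient or the scale on which the sources meet.

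Other parts of the documents bear on this:

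- **Timing of recordings.** In protocol 1.3 the Treatment Group 1 row reads "Electronic Toothbrush Data Download | | | X | X | X | X | X | X": nothing at screening or Time 1, first download at Week 4, last at Home Visit 3. The Treatment Group 2 row is the same. In 4.1, "each toothbrush stores approximately 15 days of the brushing data", and each participant receives two brushes.
- **Reported frequency.** Protocol 8.1: "The response categories will be coded as 1= Twice a day or more, 2=once a day", continuing down to 6 for never. Device frequency is continuous. For the secondary outcome, the SAP cuts reported frequency at twice a day and analyses the care partner's answer.
- **Duration.** The questionnaires described in 8.1 ask about brushing frequency. The SAP's duration outcome is a three-level hygienist rating. Reported duration is described only for the log kept by Treatment Group 2 dyads (6.1.1 and 8.1).

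**The concern.** An agreement coefficient is interpretable only if the two measurements describe the same behaviour, over about the same period, on the same scale. The baseline comparison fails on period. The frequency comparison leaves the scale open. The three-source duration comparison has no described input in Treatment Group 1.

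This analysis is the SAP's only use of the objective brushing data, which the protocol background presents as a significant feature of the study. It is also the only check on the care-partner report that supplies the brushing-frequency outcome. At most 18 + 17 = 35 dyads in the two brush groups had completed as of 05/08/24, and the SAP expects substantial device missingness. There is little room for coefficients that cannot be read.

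**Working it through.** The plan gives no agreement coefficient, threshold or sample size for this analysis, so there is no figure to reproduce.

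**1. Baseline window.**
- 4.1 and 6.1.1 place the brush at the first home visit. In Treatment Group 2 the participant first brushes with the usual brush; the hygienist will then "demonstrate the proper technique on a mouth model using a smart electronic toothbrush", and the participant tries it. Treatment Group 1 gets basic instruction in its use.
- 10.1.1 obtains written consent at that visit and requires it before intervention starts. Days available before the visit: 0 of 6.
- 8.1 puts the questionnaires before the hygienist's evaluation, so the baseline report describes brushing before the new brush.
- All six device days therefore come after the report, on a new brush and, in Treatment Group 2, after Module 1 and tailored instruction. Any difference combines reporting error with behaviour change, and the change may differ by arm.

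**2. Are post-visit days retained?** Assume the oldest records are overwritten and the Week 4 (± 7 days) download falls on day 21, 28 or 35. First day retained = max(1, download day − capacity + 1); days 1–6 kept = max(0, 6 − first day retained + 1).
- The two memories add up to 30 days: first day retained 1, 1, 6; kept 6, 6, 1.
- All brushing on one 15-day brush: first day retained 7, 14, 21; kept 0, 0, 0.

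Week 1 data can exist, but their completeness depends on how the two brushes are used.

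**3. Follow-up windows.** The last download is at Home Visit 3, so the 6-month window can only look back. At 3 months both sides are available, but in Treatment Group 2 the days after the visit follow Module 4, which is delivered at that visit. Days before the visit are the only choice that works at both visits and avoids this.

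**4. Scale, as a conditional check.** Suppose the raw code x were paired with a daily count y and every report were exactly right. For two sources and large n:
- ICC(C,1) = 2·cov / (var x + var y)
- ICC(A,1) = 2·cov / (var x + var y + (mean x − mean y)²)

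Assumed rates for codes 1 to 6 are 2, 1, 0.5, 1/7, 0.03 and 0 per day. Assumed shares are 36/40/15/5/2/2%; only the 36% comes from the protocol background. Then mean x = 2.03, mean y = 1.203, var x = 1.209, var y = 0.432, cov = −0.665.
- ICC(C,1) = −1.330 / 1.641 = −0.81
- ICC(A,1) = −1.330 / (1.641 + 0.684) = −0.57

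Across five assumed mixes (this one, 36/64, 60/30/10, 72/20/8 and uniform), ICC(A,1) runs from −0.19 to −0.97 and ICC(C,1) from −0.65 to −1.00. Reversing the code alone (7 − x) leaves ICC(A,1) at 0.03 to 0.19. With both sources cut at twice a day, every ICC is 1.00 in all five mixes.

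Cutting only the report is not enough. With assumed shares of 20/50/20/10% and rates 2, 1, 0.5 and 0.1, the 0/1 report against the count gives 0.396 / (0.160 + 0.331 + 0.656) = 0.35. With 50/35/10/5% it gives 0.595 / (0.250 + 0.401 + 0.819) = 0.40.

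**5. Duration.** Setting 8.1, 6.1.1 and the SAP side by side, Treatment Group 1 has no described dyad-reported duration. Treatment Group 2 has a log kept jointly by the dyad, so the participant and care partner are not described as separate reporters.

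**The case against.** The SAP does not prescribe pairing the raw code with a count. It says the device average is formed to align with the reports and that relevant coefficients will be computed, and its own rule for reported frequency is a cut at twice a day. A reader might infer that the planned coefficients must come out negative and discredit the care-partner report. The documents do not support that: the negative values rest on an unstated pairing and on assumed shares and rates. What stands is that no rule puts the device average on the scale of the report.

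A reader might also infer that no baseline device data can exist. That is too strong. Protocol 9.1 plans to use the Week 1 average for duration, and the SAP allows non-consecutive days. What stands is that these are post-visit data and cannot show agreement with the baseline report. The fault does not carry over to the 3- and 6-month comparisons.

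Nor is reported duration wholly unavailable. The Treatment Group 2 log records it, and 9.4.1 mentions self-reported duration. The questionnaires are summarised in the protocol rather than reproduced, so a duration item might exist. The gap lies in the described sources, chiefly for Treatment Group 1.

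Finally, the analysis is exploratory and has no decision rule, and the care-partner report is analysed whatever the result. This limits the consequence, but not the need to correct a stated window.

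**Conclusion.** The baseline part holds as a fault in a stated rule: 0 of 6 device days can precede the visit, so a baseline coefficient does not measure agreement. This rests on the brush being introduced at Home Visit 1. The schedule has no row for handing it out in the treatment groups, but 4.1, 6.1.1, the consent rule and the first download all point that way. The 3- and 6-month windows need a look-back rule.

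The scale part is missing detail, not a demonstrated error. The coefficient would be negative under perfect agreement if raw values were paired, and 1.00 if both sources were cut at twice a day. The duration part holds for Treatment Group 1 on the sources described.

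The point is worth correcting because the change is specific and cheap. It touches a supplementary analysis and alters no primary outcome.

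**What to change.** In the SAP section on electronic toothbrush data:

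1. Remove baseline from the agreement analysis. Alternatively, report those recordings only as post-visit Week 1 data, as in protocol 9.1, and not as agreement with the baseline report.
2. At 3 and 6 months, use the six days before the visit. State how a full brush behaves: if it stops recording instead of overwriting, these days are the ones at risk.
3. Put both sources on one scale before computing agreement, for example by cutting the device average at twice a day to match the secondary outcome. State the cut precisely: one missed brushing in six days gives 11/6 = 1.83, which a strict cut at 2 would class as below twice a day. Mapping the device to all six codes is less suitable, because six days cannot separate the lowest categories.
4. Name the coefficient and its form, in place of the present wording ("we will compute relevant interclass correlation coefficients to explore agreement").
5. Limit dyad-reported duration agreement to Treatment Group 2, using the log, or name another source. The hygienist's rating is made on brushing watched at the visit, so it would answer a different question.

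The cost is a few lines of SAP text and no new data collection. The losses are a baseline agreement estimate and duration agreement in Treatment Group 1; duration would rest on at most the 17 dyads completed in Treatment Group 2 as of 05/08/24.
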